1.3 Description of population

This study will be initiated in patients treated for primary breast, non-small cell lung or prostate cancer. At present there is insufficient clinical evidence and no strong biological rationale to suggest that SBRT would be effective, if at all, for some primary tumour sites and not others. Assessing efficacy overall in these prevalent tumour sites (rather than in individual primary tumour sites) at this stage will enable a positive “signal” to be identified more quickly. It is recognised that these three cancer types have different natural histories and time courses for progression. Inclusion of these three primary sites is a pragmatic decision aiming to provide a patient population that is large enough to permit adequate recruitment of patient cases and which is sufficiently homogenous to allow some conclusions with regards to the efficacy of SBRT in this context to be drawn.

1.4 Study rationale

SBRT has rapidly evolved as a radiotherapy technique over the past 5-10 years due to advances in radiation technology. In the UK, SBRT has been recently introduced into a number of specialist centres and nationally an SBRT service is being developed.

A randomised trial design is required for two reasons. Outcome data from historical cohort studies may be inherently biased as result of a highly selected patient population and other confounders. Additionally, it is important to establish prospectively the control group outcomes in contemporaneous oligometastatic patients treated with standard therapy. These are likely to represent a sub-set of patients with an improved prognosis compared to the general stage IV population and therefore extrapolation of outcome data as a comparator is unreliable.

2 TRIAL OBJECTIVES

2.1 Primary objective

To evaluate if the addition of SBRT to standard therapy improves progression free survival outcomes in patients with a limited burden of oligometastatic disease.

2.2 Secondary objectives

1. To demonstrate feasibility of recruitment to a randomised trial of SBRT plus standard therapy versus standard therapy alone.
2. To demonstrate deliverability of SBRT within dosimetric constraints.
3. To evaluate if the addition of SBRT to standard therapy improves overall survival.
4. To evaluate the acute and late toxicity associated with the addition of SBRT to standard therapy.

5. To evaluate the lesion local control rates in those receiving SBRT.
6. To compare the quality of life (QoL) in patients receiving SBRT compared to those receiving standard treatment alone.

2.3 Exploratory objectives

To evaluate if the addition of SBRT to standard therapy improves freedom from widespread metastatic disease (FFWMD).

3 TRIAL DESIGN

CORE is a phase II/III, multi-centre, non-blinded, parallel group randomised controlled trial in patients with breast, prostate or NSCLC primary cancer comparing standard of care (SOC) with or without SBRT for extra-cranial metastases. The aim of the phase II study is to demonstrate 1) feasibility of recruitment, 2) deliverability of the study in a multi-centre setting and 3) activity of SBRT, based on progression free survival, across the three tumour types. If all three aims are achieved the trial will be amended to roll into parallel tumour-site specific phase III trials.

Eligible patients are those with either primary breast, prostate or NSCLC who have presented with ≤ 3 extra-cranial, metachronous, oligometastases, all suitable for SBRT. Patients will be randomised in a 1:1 ratio to either SOC or SOC with the addition of SBRT. Choice of SOC treatment is at the discretion of the local oncologist and defined per patient prior to randomisation (see Section 9 Trial Treatment). Patients randomised to SBRT+SOC will receive a dose and fractionation regimen dependent on the metastatic site and proximity to dose limiting organs and normal tissues. Treatment will take place within 6 weeks of randomisation. The average scheme would be 3 treatments over 5 days but the maximum period of SBRT duration could be 8 treatments over 19 days.

All patients will be reviewed every 3 months with a clinical examination and tumour markers (where applicable) during years 1 and 2, and 6 monthly thereafter to 5 years. Staging and follow up imaging protocols will be tumour type dependent:

- **Breast:** 3 monthly CT scans for years 1 and 2, and 6 monthly thereafter to 5 years.
- **NSCLC:** 3 monthly CT scans for years 1 and 2, 6 monthly to year 3, then annually to 5 years.
- **Prostate:** CT scans will be performed at 6, 12 and 24 months with imaging triggered by appropriate PSA rises. A rising PSA defined as 2 successive PSA rises from nadir, measured a minimum of 4 weeks apart, will be used to trigger additional imaging (CT) between these time points.

All patients will have a toxicity assessment at each clinic visit and patient reported quality of life (QOL) assessment at 3, 6, 12, 18 and 24 months.

4 STUDY ENDPOINTS

4.1 Primary endpoint

Progression free survival.

4.2 Secondary endpoints

1. Recruitment rate and proportion of patients receiving SBRT (if allocated) in the absence of new developing widespread disease.
2. Recruitment of patients receiving SBRT within the dosimetric constraints.
3. Overall survival (OS).
4. Local lesion control.
5. Clinician reported acute and late radiation related toxicity (CTCAE version 4 and RTOG).
6. Patient reported QoL (EORTC QLQ C30 and EQ-5D questionnaire).

4.3 Exploratory endpoint

Freedom from widespread metastatic disease (FFWMD) i.e. freedom from disease not amenable to further ablative therapy (surgery, radiofrequency ablation (RFA), SBRT).

5 PATIENT SELECTION & ELIGIBILITY

5.1 Number of participants

The aim is to recruit 230 participants; 115 to SOC and 115 to SBRT + SOC. To ensure maximum feasibility information is obtained for each cohort, recruitment beyond 230 is permissible, to a maximum of 270. The decision to continue recruitment will be dependent on observed rates of accrual within each cohort and existing timelines for recruitment. Any decision to continue past 230 will be agreed in advance with the Trial Steering Committee.

5.2 Source of participants

Participants will be recruited from participating sites in the UK. Participation of sites from other countries will be dependent on adequate quality assurance and governance arrangements and on local funding. Most potential participants are likely to be identified in oncology clinics and discussed at Multi-Disciplinary Team (MDT) meetings.

5.3 Inclusion criteria

1. Age \geq 18 years
2. WHO performance status 0-2
3. Histological confirmation of primary malignancy (histological confirmation of metastasis is not mandatory but should be performed in any situation where there is diagnostic uncertainty). Patients with breast, NSCLC or prostate primary malignancies are eligible.
4. Predicted life expectancy > 6 months
5. \leq 3 metastatic lesions (total). A maximum of 2 different organ systems (e.g. liver, lung, bone, nodal) may contain metastases but the total number of lesions must not exceed 3. For example, a patient with 3 liver metastases or 1 liver metastasis and 2 lung metastases would

be eligible. A patient with 1 lung metastasis, 1 liver metastasis and an adrenal metastasis is ineligible.

6. All metastases must be visible, imaging defined targets and be suitable for treatment with SBRT in accordance with the dose fractionation options specified in the protocol. (See the associated CORE trial radiotherapy delivery guidelines for detailed SBRT guidance by metastatic site)
7. Patients who have received prior ablative therapy (e.g. surgery, RFA or SBRT) for metastatic disease are eligible, as long as this site is controlled on imaging at the point of trial entry and the total number of metastases over time since diagnosis of metastatic disease does not exceed 3. Patients with 2 or 3 metastases in which ablative therapy (e.g. surgery/RFA) to 1 site is deemed appropriate as part of standard therapy may be entered into the trial following successful delivery of the ablative treatment. Ablative therapy (e.g. surgery, RFA, cryoablation, SBRT) is not permissible as a standard of care option following randomisation for patients as part of the trial.
8. Only patients with metachronous metastatic disease presentation are eligible. Primary site must be controlled.

NSCLC patients with synchronous presentation of a single brain metastasis with the primary lung malignancy are eligible as long as both sites of disease have received radical treatment. Both primary lung site and solitary synchronous brain metastasis must be controlled at trial entry, and the total number of metastases over time including the brain metastasis must not exceed 3.

Permissible disease-free intervals are:

Breast: ≥ 6 months from completion of radical treatment including any adjuvant therapy to diagnosis of metastases. Patients who have relapsed whilst on adjuvant endocrine therapy are eligible.

NSCLC: ≥ 4 months from completion of radical treatment (not including any adjuvant chemotherapy) to diagnosis of metastases.

Prostate: ≥ 6 months from completion of radical treatment including any adjuvant therapy to diagnosis of metastases. Patients who have relapsed whilst on adjuvant endocrine therapy are eligible.

9. Only patients who are systemic therapy naïve in the metastatic setting are eligible. Prior systemic therapy in the adjuvant setting is permitted. Patients who have had a change in endocrine therapy due to the diagnosis of oligometastatic disease can be entered into the CORE trial as long as entry is within 8 weeks of this change in therapy for prostate cancer patients and within 10 weeks of this change in therapy for breast cancer patients.
10. Adequate baseline organ function to allow SBRT to all relevant targets dependent on location of metastatic subsite
11. Negative pregnancy test (for women of childbearing potential)
12. Written informed consent.

5.4 Exclusion criteria

1. Intra-cranial metastases (not meeting above inclusion criterion 8).
2. Malignant pleural effusion
3. Malignant peritoneal disease
4. Any single metastasis >6cm,(>5cm for lung metastases)

5. Prior radiotherapy to a site that precludes safe delivery of SBRT
6. Co-morbidities precluding staging or follow up imaging, or precluding procedures required to facilitate SBRT
7. Loco-regional nodal relapse where surgery is considered the standard of care and is technically feasible. Patients with internal mammary chain or supraclavicular fossa lymph node relapses of breast cancer are eligible if SBRT dose constraints can be met. Patients with axillary nodal relapse from breast cancer are excluded
8. Spinal cord compression, or impingement of the cord or any other situation whereby the clinician feels that urgent radiotherapy to the spine is required (within 24 hours)
9. Any condition or significant clinical co-morbidities that preclude the safe delivery of SBRT (e.g. history of clinically significant diffuse interstitial lung disease if SBRT to lung metastases or lesions adjacent to lungs are considered or clinically significant colitis i.e. ulcerative colitis /Crohn's disease if SBRT to the pelvis or abdomen is considered).
10. Prostate cancer patients who have relapsed on Androgen Deprivation Therapy (ADT) which was started for biochemical relapse without staging investigations to define their relapse status, or who have relapsed on CAB which was started for biochemical relapse.
11. Prostate cancer patients receiving or have previously received abiraterone, enzalutamide or chemotherapy e.g. docetaxel.
12. Previous malignancy within the last 2 years (except basal cell carcinoma or squamous cell carcinoma of the skin), or if previous malignancy is expected to significantly compromise 5 year survival.
13. Patients whose entry to the trial will cause unacceptable clinical delays to their planned management.
14. Any psychological, familial, sociological or geographical condition potentially hampering compliance with the study protocol and follow-up schedule.

5.5 Life style guidelines

All female participants (including SOC patients as SOC may also involve non-high dose RT) must be surgically sterile or be post-menopausal, or must agree to use effective contraception during the period of therapy only.

All male participants (including SOC patients as SOC may also involve non-high dose RT) must be surgically sterile or must agree to use effective contraception during the period of therapy only.

Effective contraception is defined as double barrier contraception (e.g. condom plus spermicide in combination with a diaphragm, cervical cap or intrauterine device).

6 SCREENING

6.1 Screening log

All participating sites will be required to keep a log of all participants with either primary breast, prostate or NSCLC who have presented with oligo-metastatic disease (≤ 3 metastases or sites) that are potentially eligible for this study. The information collected on the log will include:

- Date patient identified
- Screening outcome (patient approached/accepted participation/declined participation)

- Reasons for not approaching / declining participation (if available)
- Trial ID (if applicable)
- Basic primary tumour characteristics (ER and HER2 status for breast, EGFR status for NSCLC and castrate status for prostate cancer patients).

This information will be used by the TMG to monitor recruitment activity and will inform phase III study planning. No patient identifiable data will be sent to ICR-CTSU at this stage.

6.2 Procedure for obtaining informed consent

The Principal Investigator (or designated individual) must ensure that each trial patient is fully informed about the nature and objectives of the trial and possible risks associated with participation. Participants should be given the current ethics approved CORE patient information sheet for their consideration. Patients should only be asked to consent to the study after they have had sufficient time to consider the trial, and the opportunity to ask any further questions.

No protocol specified assessments should be conducted until the CORE consent form has been signed and dated by both the patient and the Investigator, unless they are performed routinely as part of standard patient care.

Molecular biomarker and imaging translational sub-studies are planned subject to confirmation of funding and subsequent ethics approval. Patients will be made aware that participation in such sub-studies is entirely voluntary and refusal to participate will not result in ineligibility to participate in the main clinical trial and will not impact the medical care received.

Confirmation of the patient's consent and the informed consent process (including the date of consent) must be documented in the patient's medical notes. A copy of the signed consent form should be provided to the patient and the original retained in the investigator site file, which must be available for verification by ICR-CTSU study staff at any time.

6.3 Participation in other clinical trials

Patients who fulfil the eligibility criteria will be given the opportunity to participate in CORE if they have participated in other clinical trials prior to recruitment.

Participation in other clinical trials post-randomisation into CORE will be considered on a case by case basis by the Trial Management Group.

7 RANDOMISATION

Patients must be randomised centrally by the trials unit (ICR-CTSU) before trial treatment can commence.

Patients should be randomised by telephoning ICR-CTSU on:

[name]

09.00-17.00 (UK time) Monday to Friday

For non UK patients, randomisation outside of UK office hours should be requested by faxing the ICR-CTSU on:

[contact].00-17.00 (UK time) Monday to Friday

Further details of randomisation procedures for non-UK patients will be detailed in the relevant country specific group appendix.

Randomisation should take place as close to the planned start date of treatment as possible. Treatment allocation will be by minimisation (with a random component). An eligibility and randomisation checklist must be completed prior to randomisation.

The following information will be required at randomisation:

- Name of hospital, consultant, name of QA approved clinician to deliver SBRT to specific metastatic site and person registering patient
- Confirmation that patient has given written informed consent for trial and for any sub-studies
- Confirmation that patient is eligible for the trial by completion of the eligibility checklist
- Patient's full name, hospital number, date of birth, postcode and NHS/CHI number (or equivalent for international participants)
- Site of primary tumour (breast, NSCLC, prostate)
- Basic primary tumour characteristics including ER status for breast cancer; EGFR status for NSCLC if known; Endocrine therapy naïve (includes patients who have started endocrine therapy in the 8 weeks prior to randomisation) vs castrate resistant for prostate cancer patients
- Details of planned standard of care including type and duration
- Sites of metastatic disease

The caller will be given the patient's unique randomisation number (Trial ID) and treatment allocation.

ICR-CTSU will send written confirmation of randomisation via email to the relevant personnel at the recruiting site to confirm a patients' entry into the trial.

8 TRIAL ASSESSMENTS

All trial specific assessments must be completed after the patient has given informed consent.

8.1 Pre-randomisation

All assessments should be conducted within 42 days prior to randomisation.

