8.1.1 All patients

- Histological confirmation of primary breast, prostate or NSCLC*
- Complete medical history
- Physical examination including WHO performance status, body weight, height, blood pressure
- Negative pregnancy test (for women of childbearing potential)
- Baseline tumour assessment.

* Will be before 42 days prior to randomisation

The following are required to evaluate if patients are suitable for SBRT to the relevant metastatic subsite:

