8.2 Pre-Treatment assessments

The following assessments should be conducted once patient eligibility has been confirmed:

- Full blood count, urea and electrolytes, LFTs (and clotting screen (INR) for patients with liver metastases)
- Assessment of baseline symptoms using NCI CTCAE v.4.0 and RTOG and concomitant medications taken from 30 days prior to randomisation
- Baseline quality of life questionnaire (EORTC QLQ C30 and EQ5D) (should be before treatment allocation is known to the patient).

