8.8 Schedule of assessments

| Visit/Assessments/ Procedures | Pre-randomisation | Pre-treatment | End of trial treatment for SBRT + SOC group or equivalent for SOC group | Time from randomisation | | | | | | | | | | | | | |
|--|-------------------|---------------------------------------|---|-------------------------|-----|------------------|------|------------------|------------------|------------------|------|------------------|------------------|----------------|------------------|----------------|------------------|
| | Within 42 days | Following confirmation of eligibility | SBRT + SOC group: within +/- 7days of last SBRT treatment SOC only group: within 6 weeks after randomisation | 3 M | 6 M | 9 M | 12 M | 15 M | 18 M | 21 M | 24 M | 30 M | 36 M | 42 M | 48 M | 54 M | 60 M |
| Informed consent | X | | | | | | | | | | | | | | | | |
| Histological confirmation of primary breast, prostate or NSCLC | X* | | | | | | | | | | | | | | | | |
| Complete medical history | X | | | | | | | | | | | | | | | | |
| Physical examination including WHO performance status, body weight, height, blood pressure (BP at baseline only) | X | | X | X | X | X | X | X | X | X | X | X | X | X | X | X | X |
| Tumour primary assessment using RECIST v.1.1 criteria | X | | | X ^{B,L} | X | X ^{B,L} | X | X ^{B,L} | X ^{B,L} | X ^{B,L} | X | X ^{B,L} | X ^{B,L} | X ^B | X ^{B,L} | X ^B | X ^{B,L} |
| Concomitant therapy assessment | | X | X | | | | | | | | | | | | | | |
| Full blood count, urea and electrolytes, LFTs | | X | | | X | | | | | | | | | | | | |
| Pregnancy test (for women of childbearing potential) | X | | | | | | | | | | | | | | | | |
| Symptom assessment using NCI | | X | X | X | X | X | X | X | X | X | X | X | X | X | X | X | X |

| Visit/Assessments/ Procedures | Pre-randomisation | Pre-treatment | End of trial treatment for SBRT + SOC group or equivalent for SOC group | Time from randomisation | | | | | | | | | | | | | |
|---|-------------------|---------------------------------------|---|-------------------------|----------------|----------------|----------------|----------------|----------------|----------------|----------------|----------------|----------------|----------------|----------------|----------------|----------------|

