9.1.1 Treatment timelines

To allow sufficient time for treatment planning, SBRT can commence up to 6 weeks after randomisation.

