9.2 Standard of care treatment

Standard of care (SOC) is at the discretion of the local oncologist and will be defined for each patient at trial entry. The SOC treatment specified at randomisation should be administered irrespective of what arm the patient is randomised to (with the exception that palliative radiotherapy would not be administered if the patient was randomised to SBRT+SOC). It may include any standard therapy that is clinically appropriate: chemotherapy (including maintenance where appropriate), biological therapy, endocrine therapy, palliative radiotherapy ($\text{BED}_{10} \leq 40$ i.e. equivalent to 30Gy in 10 fractions or less) or observation or any combination of these. As indicated in the eligibility criteria, patients for whom standard of care would be ablative therapy (e.g. surgery, RFA, cryoablation) are not eligible for CORE participation.

If allocated to SOC only group, SOC treatment may begin on the same day of randomisation or as soon as possible after randomisation. If allocated to SBRT+ SOC group, SBRT will precede SOC with the exception of endocrine therapy which may be initiated following randomisation and be given concurrently with the SBRT. All patients should commence SOC therapy within 4 weeks of SBRT finishing.

For patients where a change in endocrine therapy preceded trial entry (within 8 weeks of randomisation for prostate cancer patients and within 10 weeks of randomisation for breast cancer patients) it should be stated at trial entry whether endocrine therapy will be the only SOC treatment or whether palliative radiotherapy will also be offered (if known at this point).

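### The only scheduled pregnancy test is tied to randomisation, so the protocol permits a test up to 84 days old at the first SBRT fraction, and contraception is not clearly required over that interval

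*Protocol*

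**What the plan says.** A negative pregnancy test is an entry condition for women of childbearing potential (Protocol 5.3, criterion 11). Section 8.1.1 places it in the pre-randomisation set, for which 8.1 states: "All assessments should be conducted within 42 days prior to randomisation". Only histology is exempted from that window. The schedule in 8.8 marks the pregnancy test once, in the pre-randomisation column.

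On the start of treatment, 9.1.1 says that "SBRT can commence up to 6 weeks after randomisation". Section 3 gives the same six weeks.

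Section 8.2 opens with "The following assessments should be conducted once patient eligibility has been confirmed" and lists blood counts, biochemistry, clotting for liver metastases, baseline symptoms, concomitant medication and quality of life. It lists no pregnancy test.

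On contraception, 5.5 says that participants who are not sterile or post-menopausal "must agree to use effective contraception during the period of therapy only". The start of that period is not defined. Under 9.2, standard of care may be active treatment "or observation or any combination of these", and in the experimental arm "SBRT will precede SOC with the exception of endocrine therapy which may be initiated following randomisation".

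**The concern.** The test serves two purposes: it establishes eligibility, and it protects against irradiating an unrecognised pregnancy. Timing it to randomisation serves the first. The second depends on how old the result is when SBRT begins, and the protocol sets no limit on that directly. The limit is simply the sum of two windows written for other reasons: a screening window and a radiotherapy planning window.

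A pregnancy that begins after the screening test would not be picked up by any step in the protocol's own schedule before ablative radiotherapy. The instructions to stop treatment act only once the pregnancy is known. Contraception could make the age of the test less important, but only if it were clearly required from the test onwards.

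The protocol does not leave all pre-SBRT safety checks to local practice. It requires bloods before treatment in 8.2, and 9.2.1 requires stop dates for tyrosine kinase inhibitors and radiosensitiser information to be recorded before SBRT. The pregnancy test is not among the checks it repeats.

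**Working it through.** The protocol states no figure for the age of the test at SBRT, so there is none to reproduce. The check is calendar arithmetic plus a comparison of sections.

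**Inputs**
- Test window: up to 42 days before randomisation (8.1, 8.1.1, 8.8).
- SBRT start: up to 6 weeks after randomisation, i.e. 6 × 7 = 42 days (9.1.1; also section 3).
- Further tests before the first fraction: none listed (8.2, 8.8).

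**Age of the test at the first fraction**

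Age = (days from test to randomisation) + (days from randomisation to first fraction).

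| Test taken | SBRT starts | Age of test |
|---|---|---|
| 42 days before randomisation | 42 days after | 42 + 42 = 84 days |
| Day of randomisation | 42 days after | 0 + 42 = 42 days |

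The permitted maximum is 84 days. When SBRT starts at its limit, the age lies between 42 and 84 days however promptly the test was done.

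**Text that might shorten the interval**
- Section 7 asks for randomisation as near as possible to the planned treatment start. It gives no number of days, and 9.1.1 expressly grants six weeks for planning.
- Appendix A1.2 asks for every effort to finish screening evaluations within 4 weeks (28 days) before treatment. It sits in the RECIST appendix under baseline lesion documentation, states an aim, and does not replace the 42-day rule in 8.1. If it were read to cover every screening test, the permitted maximum would be 84 / 28 = 3 times that aim.

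**Contraception over the same interval**
- Section 5.5 applies to standard-of-care patients as well, so the period of therapy is wider than SBRT delivery.
- A woman on endocrine therapy may have started it after randomisation (9.2) or, with breast cancer, changed it up to 10 weeks (70 days) before entry (5.3, criterion 9). On the wider reading she is covered for some or all of the interval.
- A woman allocated SBRT whose standard of care is observation has no therapy before the first fraction. One whose standard of care is chemotherapy receives it after SBRT (9.2). For both, therapy most naturally begins at the first fraction, which leaves the interval uncovered.
- On any reading, the days between the test and randomisation are not clearly covered unless therapy had already begun.

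**Repeat courses (secondary)**

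Section 9.1.6 requires more than 3 months since the last SBRT. The entry test precedes the first course, so at any repeat course it is more than 3 months old. Section 9.1.6 sets conditions on lesion number, size, disease control and composite dose, but none on pregnancy.

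**The case against.** The strongest reply is that the protocol already deals with pregnancy. Section 8.5 lists it as a reason to discontinue trial treatment. Section 10.1 says a pregnancy arising during trial participation should be followed up, and that reaches the interval before the first fraction. Section 10.10 adds reporting and immediate discontinuation. This stands for a known pregnancy. A reader might infer from the wording of 10.10, which starts at receipt of SBRT, that an earlier pregnancy goes unfollowed. Section 10.1 rules that out. None of these sections detects a pregnancy that nobody knows about.

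A second reply is that the Radiotherapy Planning and Delivery Guidelines, which 9.1.2 makes binding and which are not available here, may require a check before irradiation. This also stands. It would be wrong to infer that patients go untested. What can be said is that the protocol itself neither requires nor cross-references a later test.

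Third, 84 days needs both windows used to the full, against the advice in section 7. That is fair: it is a permitted maximum, not an expected interval. The 42-day figure, however, needs only the planning window.

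Fourth, the contraception wording is ambiguous rather than absent, and for many women on endocrine therapy it may suffice. The point is therefore confined mainly to women on observation or post-SBRT chemotherapy.

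Finally, 8.4 leaves care at progression to local judgement, so the lack of a scheduled visit before repeat SBRT is expected. That weakens the repeat-course point, but 9.1.6 still sets its own conditions for those courses.

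**Conclusion.** The point holds as a participant-safety gap. Followed exactly, the protocol allows a woman of childbearing potential to start ablative radiotherapy on a pregnancy test up to 84 days old, and at least 42 days old if SBRT starts at its limit. Contraception is not clearly required across that interval for every such woman. The gap is in detecting an unknown pregnancy, not in managing a known one.

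The affected group is small and the protocol does not quantify it: women of childbearing potential with breast cancer or NSCLC who are allocated SBRT. A reader might try to derive a ceiling from the planned mix in 11.1.2: (0.14 + 0.11) × 230 / 2 = 28.75, about 29. That is not a true upper bound. The same section allows up to 270 patients so that each cohort can reach at least 50, which would give about (50 + 50) / 2 = 50 non-prostate patients on SBRT. Both figures also include men with NSCLC and post-menopausal women, so neither estimates the number at risk.

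The conclusion assumes that the schedule in 8.8 is complete as shown and makes no claim about the unseen guidelines. No endpoint, analysis or decision rule is affected.

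**What to change.** - **8.2 and the pre-treatment column of 8.8:** require a negative pregnancy test shortly before the first SBRT fraction for women of childbearing potential allocated SBRT. Tie it explicitly to the first fraction, because that column is currently anchored only to confirmed eligibility. The clinical team should choose the interval. If the Radiotherapy Planning and Delivery Guidelines already require such a test, a cross-reference is enough.
- **5.5:** state that contraception runs from the screening test to the end of therapy, including any repeat SBRT course.
- **9.1.6 (secondary):** apply the same test condition, or cross-reference, to each repeat course.

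The editing cost is one mark in 8.8, one line each in 8.2 and 9.1.6, and one clause in 5.5. The burden is one simple repeat test per SBRT course in a small group, with no additional testing if the guidelines already provide for it. The contraception clause adds no procedure.
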